## **10. ETHICAL CONSIDERATIONS AND ADMINISTRATIVE PROCEDURES**

### **10.1. Investigator Responsibilities**

This study will be performed in accordance with ethical principles that originate in the Declaration of Helsinki and conducted in adherence to the study Protocol; GCPs as defined in Title 21 of the US CFR Parts 11, 50, 54, 56, and 312; ICH E6 GCP consolidated guidelines; and local regulatory requirements as applicable to the study locations.

The investigator will be responsible for:

- Permitting study-related monitoring, sponsor audits, IRB/IEC review, and regulatory inspections by providing direct access to source data and other relevant clinical study documents.
  - Monitoring: Qualified representatives of the sponsor or its designee, study monitors, will monitor the study according to a predetermined plan. The investigator must allow the study monitors to review any study materials and subject records at each monitoring visit.
  - Auditing: Qualified representatives of the sponsor or its designee may audit the clinical study site and study data to evaluate compliance with the Protocol, applicable local clinical study regulations, and overall study conduct. The investigator must allow the auditors to review original source records and study documentation for all subjects.
  - Regulatory inspection: Regulatory authorities may conduct an inspection of the study and the site at any time during the development of an investigational product. The investigator and staff are expected to cooperate with the inspectors and allow access to all source documents supporting the eCRFs and other study-related documents. The investigator must immediately notify the sponsor when contacted by any regulatory authority for the purposes of conducting an inspection.
- Obtaining informed consent and ensuring that the study subjects' questions have been answered and the subjects fully understand study procedures:
  - Informed consent must be obtained before any study-related procedures are conducted, unless otherwise specified by the Protocol.

- Informed consent must be obtained using the IRB/IEC-approved version in a language that is native and understandable to the subject. A template will be provided by the sponsor or its designee. The sponsor or its designee must review and acknowledge the site-specific changes to the ICF template. The ICF must include a statement that the sponsor or its designee and regulatory authorities have direct access to subject records.
- Obtaining approval from the IRB/IEC before the start of the study and for any changes to the clinical study Protocol, important Protocol deviations, routine updates, and safety information in accordance with institutional requirements and local law.
  - The investigator is responsible for ensuring that the safety reports provided by the sponsor are reviewed and processed in accordance with regulatory requirements and with the policies and procedures established by the IRB/IEC.
- Adhering to the Protocol as described in this document and agreeing that changes to the Protocol procedures, with the exception of medical emergencies, must be discussed and approved, first, by the sponsor or its designee and, second, by the IRB/IEC. Each investigator is responsible for enrolling subjects who have met the specified eligibility criteria.
- Retaining records in accordance with all local, national, and regulatory laws, but for a minimum period of at least 2 years after the last marketing application approval in an ICH region and until there are no pending or contemplated marketing applications in an ICH region, or if not approved, 2 years after the termination of the test article for investigation to ensure the availability of study documentation should it become necessary for the sponsor or a regulatory authority to review.
  - The investigator must not destroy any records associated with the study without receiving approval from the sponsor. The investigator must notify the sponsor or its designee in the event of accidental loss or destruction of any study records. If the investigator leaves the institution where the study was conducted, the sponsor or its designee must be contacted to arrange alternative record storage options.
  - All eCRF data entered by the site (including audit trail), as well as computer hardware and software (for accessing the data), will be maintained or made available at the site in compliance with applicable record retention regulations. The sponsor will retain the original eCRF data and audit trail.

## **10.2. Accountability, Handling, and Disposal of Study Drug**

The investigator is responsible for drug accountability at the study site; however, some of the drug accountability duties may be assigned to an appropriate pharmacist or other designee. Inventory and accountability records must be maintained and readily available for inspection by the study monitor and are open to inspection at any time by any applicable regulatory authorities. The investigator or designee must maintain records that document:

- Delivery of study drug to the study site.
- Inventory of study drug at the site.

- Subject use of the study drug including pill or unit counts from each supply dispensed.
- Return of study drug to the investigator or designee by subjects.

The investigational product must be used only in accordance with the Protocol. The investigator will also maintain records adequately documenting that the subjects were provided the specified study drug. These records should include dates, quantities, and any available batch or serial numbers or unique code numbers assigned to the investigational product and study subjects.

Completed accountability records will be archived by the site. The investigator or designee will be expected to collect and retain all used, unused, and partially used containers of study drug until verified by the study monitor (unless otherwise agreed to by the sponsor). At the conclusion of the study, the investigator or designee will oversee shipment of any remaining study drug back to the sponsor or its designee for destruction according to institutional standard operating procedures. If local procedures mandate on-site destruction of investigational supply, the site should (where local procedures allow) maintain the investigational supply until the study monitor inspects the accountability records in order to evaluate compliance and accuracy of accountability by the investigative site. At sites where the study drug is destroyed before monitor inspection, the monitors rely on documentation of destruction per the site SOP.

### **10.3. Data Management**

Data management will be performed in a validated database via an Electronic Data Capture (EDC) system. All data entry, verification, and validation will be performed in accordance with the current standard operating procedures of the Data Management Department at the sponsor or its designee. The database will be authorized for lock once all defined procedures are completed.

The investigator will be provided with access to an EDC system so that an eCRF can be completed for each subject. Entries made in the eCRF must be verifiable against source documents; if updates to the database are not possible, any discrepancies should be explained and documented. The investigator will be responsible for reviewing all data and eCRF entries, and will sign and date the designated forms in each subject's eCRF, verifying that the information is true and correct. The investigator is responsible for the review and approval of all query responses.

Protocol deviations will be identified and recorded in the Protocol Deviation form of the eCRF. The study monitor will reference the Monitoring Plan in order to ensure that each issue identified is appropriately documented, reported, and resolved in a timely manner in accordance with the plan's requirements.

### **10.4. Data Privacy and Confidentiality of Study Records**

The investigator and the sponsor or its designee must adhere to applicable data privacy laws and regulations. The investigator and the sponsor or its designee are responsible for ensuring that sensitive information is handled in accordance with local requirements (eg, HIPAA). Appropriate consent and authorizations for use and disclosure and/or transfer (if applicable) of protected information must be obtained.

Subject names will not be supplied to the sponsor or its designee, if applicable. Only the subject number and subject's initials (subject's initials will only be recorded if allowable by local regulations) will be recorded in the eCRF, where permitted; if the subject's name appears on any other document (eg, laboratory report), it must be obliterated on the copy of the document to be supplied to the sponsor or its designee. Study findings stored on a computer will be stored in accordance with local data protection laws. The subjects will be informed that representatives of the sponsor or its designee, IRB or IEC, or regulatory authorities may inspect their medical records to verify the information collected, and that all personal information made available for inspection will be handled in strictest confidence and in accordance with local data protection laws.

## **10.5. Financial Disclosure**

Before study initiation, all clinical investigators participating in clinical studies subject to FDA Regulation Title 21 CFR Part 54 – Financial Disclosure by Clinical Investigators (ie, "covered studies") are required to submit a completed Clinical Investigator Financial Disclosure form that sufficiently details any financial interests and arrangements that apply. For the purpose of this regulation, "clinical investigator" is defined as any investigator or subinvestigator who is directly involved in the treatment or evaluation of research subjects, including the spouse and each dependent child of the clinical investigator or subinvestigator. These requirements apply to both US and foreign clinical investigators conducting covered clinical studies.

Any new clinical investigators added to the covered clinical study during its conduct must also submit a completed Investigator Financial Disclosure Form. During a covered clinical study, any changes to the financial information previously reported by a clinical investigator must be reported to the sponsor or its designee. At the conclusion of the covered clinical study, the clinical investigators will be reminded of their obligations. In the event that the clinical investigator is not reminded, they nevertheless will remain obligated to report to the sponsor or its designee any changes to the financial information previously reported, as well as any changes in their financial information for a period of 1 year after completion of the covered clinical study.

## **10.6. Publication Policy**

By signing the study Protocol, the investigator and his or her institution agree that the results of the study may be used by the sponsor, Incyte Corporation (Incyte), for the purposes of national and international registration, publication, and information for medical and pharmaceutical professionals. Study results will be published in accordance with applicable local and national regulations. If necessary, the authorities will be notified of the investigator's name, address, qualifications, and extent of involvement. The terms regarding the publication of study results are contained in the agreement signed with the sponsor or its designee. A signed agreement will be retained by the sponsor or its designee.

## APPENDIX A. INFORMATION REGARDING EFFECTIVENESS OF CONTRACEPTIVE METHODS

### For Subjects Participating in the Study:

The following methods that can achieve a failure rate of less than 1% per year when used consistently and correctly are considered as highly effective birth control methods.

Such methods include:

- Combined (estrogen and progestogen containing) hormonal contraception associated with inhibition of ovulation
  - oral
  - intravaginal
  - transdermal
- Progestogen-only hormonal contraception associated with inhibition of ovulation
  - oral
  - injectable
  - implantable
- Intrauterine device (IUD)
- Intrauterine hormone-releasing system (IUS)
- Bilateral tubal occlusion
- Vasectomised partner
- Sexual abstinence

 Hormonal contraception may be susceptible to interaction with the IMP, which may reduce the efficacy of the contraception method.

 Contraception methods that in the context of this guidance are considered to have low user dependency.

 Vasectomised partner is a highly effective method provided of avoiding pregnancy that partner is the sole sexual partner of the WOCBP trial participant and that the vasectomised partner has received medical assessment of the surgical success.

 In the context of this guidance, sexual abstinence is considered a highly effective method only if defined as refraining from heterosexual intercourse during the entire period of risk associated with the study treatments. The reliability of sexual abstinence needs to be evaluated in relation to the duration of the clinical trial and the preferred and usual lifestyle of the subject.

Source: [CTFG 2014](#).

## APPENDIX B. POTENT CYP2D6 INHIBITORS AND POTENT CYP3A4 INHIBITORS AND INDUCERS

### *In Vivo* CYP2D6 Potent Inhibitor

Inhibitor	Therapeutic Class
Quinidine	antiarrhythmic
Fluoxetine	Antidepressants
Dacomitinib	Kinase inhibitors
Ecstasy	Recreational drug
Paroxetine	Antidepressant
Bupropion	Antidepressant

### *In Vivo* CYP3A4 Potent Inhibitors

Inhibitor	Therapeutic Class
Indinavir/RIT)	Protease inhibitor
Tipranavir/RIT	Protease inhibitor
Ritonavir	Protease inhibitor
Cobicistat (GS-9350)	None
Indinavir	Protease inhibitor
Ketoconazole	Antifungal
Troleandomycin	Antibiotics
Telaprevir	Antivirals
Danoprevir/RIT	Antivirals
Elvitegravir/RIT	Treatments of AIDS
Saquinavir/RIT	Protease inhibitors
Lopinavir/RIT	Protease inhibitors
Itraconazole	Antifungals
Voriconazole	Antifungals
Mibepradil	Calcium channel blocker
LCL161	Cancer treatment

### ***In Vivo* CYP3A4 Potent Inhibitors (Continued)**

Inhibitor	Therapeutic Class
Clarithromycin	Antibiotics
Posaconazole	Antifungals
Telithromycin	Antibiotics
Grapefruit juice DS	Food products
Conivaptan	Diuretics
Nefazodone	Antidepressants
Nelfinavir	Protease inhibitors
Saquinavir	Protease inhibitors
Idelalisib	Kinase inhibitors
Boceprevir	Antivirals

### ***In Vivo* CYP3A4 Potent Inducers**

Inducers	Therapeutic Class
Rifampin	Antibiotics
Mitotane	Other antineoplastics
Avasimibe	Other antilipemics
Phenytoin	Anticonvulsants
Carbamazepine	Anticonvulsants
Enzalutamide	Antiandrogens
St John's Wort	Herbal medications
Rifabutin	Antibiotics
Phenobarbital	Anticonvulsants

Source: University of Washington School of Pharmaceutics: Drug Interaction Database Program. 2002.  
<http://www.druginteractioninfo.org>.

## APPENDIX C. PHARMACOKINETIC ANALYTICAL PARAMETERS

$C_{ave}$	Average steady-state plasma concentration ( $AUC_{0-12h}/12h$ or $AUC_{0-24h}/24h$ )
$C_{max}$	Maximum observed plasma concentration
$C_{min}$	Minimum observed plasma concentration during the dosing interval
$T_{max}$	Time to maximum plasma concentration
$AUC_{0-t}$	Area under the single-dose plasma concentration-time curve from Hour 0 to the last quantifiable measurable plasma concentration, calculated by the linear trapezoidal rule for increasing concentrations and the log trapezoidal rule for decreasing concentrations
$AUC_{0-\tau}$ (ie, $AUC_{0-12h}$ or $AUC_{0-24h}$ )	Area under the steady-state plasma concentration-time curve over 1 dosing interval calculated by the linear trapezoidal rule for increasing concentrations and the log trapezoidal rule for decreasing concentrations
$\lambda_z$	Apparent terminal phase disposition rate constant, where $\lambda_z$ is the magnitude of the slope of the linear regression of the log concentration versus time profile during the terminal phase
$t_{1/2}$	Apparent plasma terminal phase disposition half-life (whenever possible), where $t_{1/2} = (\ln 2) / \lambda_z$
$Cl/F$	Oral dose clearance
$V_z/F$	Apparent oral dose volume of distribution
Fluctuation	Steady-state fluctuation ( $[C_{max} - C_{min}] / C_{ave}$ )

In addition, the following PK parameters may be calculated, whenever possible, for each subject based on the urine INCB059872 concentrations:

$A_e$	Amount of drug excreted in the urine over sampling interval
$Cl_r$	Renal clearance, where $Cl_r = A_e/AUC$
% Excreted or $f_e$	percent excreted in the urine, where % Excreted = 100 ( $A_e/dose$ )

Pharmacokinetic calculations will be performed, if appropriate, using commercial software such as WinNonlin®. Additional details of analyses will be described in the statistical analysis plan.

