#### 4.1.1. Monotherapy Dose Escalation (Part 1)

Approximately 24 subjects will be enrolled into each dose-escalation treatment group.

Treatment Group A will enroll subjects with AML or MDS. The enrollment in TG B is prioritized for SCLC. Enrollment of subjects with other solid malignancies (eg, endocrine tumors) is allowed with the sponsor medical monitor approval.

Dose escalation for TG A and TG B in Part 1 will proceed independently, with each treatment group following a 3 + 3 design. The starting dose of INCB059872 for TG A and TG B will be 2 mg QOD. A minimum of 3 subjects will initially be enrolled in each treatment group in Part 1, and each subject will be observed for a DLT observation period of 1 cycle (28 days) before the next dose cohort begins enrollment. Subjects must have taken at least 75% of the cohort-specific dose (at least 11 doses for QOD schedule or at least 21 doses for QD schedule) in the first 28 days of study treatment or have had a DLT to be considered evaluable. Subjects who are not evaluable will be replaced. The dose will be escalated by up to 100% if none (0) of the first 3 evaluable subjects enrolled has a DLT. Dose escalation should proceed in smaller increments (ie, by no more than 50%) if a DLT is observed, or if 2 or more subjects at a given dose level experience Grade 2 or higher AEs (unless they are clearly and incontrovertibly due to an alternative cause).

If 1 of the first 3 evaluable subjects enrolled has a DLT, the cohort will be expanded to include 3 additional evaluable subjects, and if no DLT occurs in the additional 3 subjects, then the dose will be escalated by up to 100%. Otherwise, if 2 subjects in a cohort of 3 or 6 subjects experience DLTs, the MTD will be deemed to be exceeded. An interim lower dose level may be explored if the dose increment has been 100%. The MTD will be defined as 1 dose level below

the dose level at which one-third or more subjects experience DLTs. Upon the aggregate review of overall safety, PK, [REDACTED] and efficacy, a recommended dose (per tumor type) will be determined to maximize the clinical benefit/risk margin.

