## **5. TREATMENT**

INCB059872 will be self-administered orally QOD or QD on a 28-day cycle. In each cycle of the QOD dosing schedule, subjects should receive 14 doses of INCB059872. In each cycle of the QD dosing schedule, subjects should receive 28 doses of INCB059872. Tablets will be available in 1 mg strength. The initial starting dose for Part 1 will be 2 mg QOD. The initial starting dose for other parts of the study will be based on the aggregate data review of Part 1.

For QOD administration, if a dose is missed by more than 24 hours, the subject should skip the dose and take the next scheduled dose at the usual time. For QD administration, if a dose is missed by more than 4 hours, the subject should skip the dose and take the next scheduled dose at the usual time. INCB059872 tablets should be taken on an empty stomach if possible (refrain from food consumption during the period 2 hours before and 1 hour after taking INCB059872). For subjects participating in the food-effect portion of the study in Part 2, TG B1, a high-fat, high-calorie meal will be consumed within 30 minutes before taking INCB059872 on Cycle 2 Day 1.

Alternative dosing regimens (ie, QD) may be explored based on emerging PK/█ and safety data.

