### 7.8.3. Bioanalytical Methodology and Analysis

The plasma samples will be analyzed for INCB059872 by a validated liquid chromatography–tandem mass spectrometry assay. If there is sufficient urinary excretion of unchanged INCB059872 for assay, the urine samples will be assayed for INCB059872 by a validated assay.

Pharmacokinetic parameters that will be analyzed are shown in [Appendix C](#), and the analysis methodology is described in Section [9.4.2](#).

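### Appendix C defines average concentration only over 12 h or 24 h; taken literally, it about doubles C_ave and halves Fluctuation for every-other-day dosing

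*Protocol*

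**What the plan says.** Protocol Appendix C lists C_ave as "Average steady-state plasma concentration" and gives two ways to compute it: the 0-12 h AUC over 12 h, or the 0-24 h AUC over 24 h. There is no 48 h form and no general tau form. AUC0-tau is described as "Area under the steady-state plasma concentration-time curve over 1 dosing interval", but the label beside it restricts it, with an ie, to the same 12 h and 24 h windows. Fluctuation is the difference between Cmax and Cmin divided by C_ave.

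Protocol Section 5 states: "In each cycle of the QOD dosing schedule, subjects should receive 14 doses of INCB059872". QOD is a main schedule in this study:

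- Part 1: "The starting dose of INCB059872 for TG A and TG B will be 2 mg QOD" (Protocol Section 4.1.1). In Protocol Table 1, 19 of the 39 treated subjects were in QOD cohorts (3 in TG A; 3 + 6 + 7 = 16 in TG B).
- Part 2: TG A2, B1 and B2 are assigned 3 mg QOD (Protocol Section 4.1.2).
- Part 3: TG E starts at 3 mg QOD (Protocol Section 4.1.3).

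These parameters are in scope. Protocol Section 7.8.3 says "Pharmacokinetic parameters that will be analyzed are shown in" Appendix C. Appendix C leaves further detail to the SAP, but SAP Section 8 refers back to Appendix C and defines no dosing interval.

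**The concern.** C_ave is meant to be the mean concentration over a full dosing interval. For a QOD subject, the 24 h form is a correct mean over the first 24 h only. With a half-life of a few hours, the second 24 h adds almost nothing to the AUC but should still count in the denominator. The error affects QOD and leaves QD untouched, so a table setting the two schedules side by side would show a difference in C_ave and Fluctuation that comes from the definition and not from the drug. The protocol also departs from its own usage: Sections 1.2.2 and 1.6.1 express the QOD exposure projection as AUC0-48.

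**Working it through.** The plan states no C_ave value, so there is no figure to reproduce. The check asks what the written rule returns for a QOD subject.

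**Inputs**

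- QOD interval, from the dose count in Protocol Section 5: 28 × 24 / 14 = 48 h. For QD, 28 × 24 / 28 = 24 h.
- Half-life T: about 3 h, an allometric projection (Protocol Section 1.2.2). Other values below are assumptions.
- Projected steady-state exposure at 2 mg QOD: AUC0-48 about 0.2 µM·h and Cmax about 0.05 µM (Protocol Section 1.2.2). As a consistency check, 0.05 × 3 / ln 2 = 0.216 µM·h, which agrees with 0.2 to one significant figure under mono-exponential decay and immediate absorption.

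**Step 1: the 24 h form against the true QOD mean**

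Ratio = (AUC0-24/24) / (AUC0-48/48) = 2 × (1 − 2^(−24/T)) / (1 − 2^(−48/T)) = 2 / (1 + 2^(−24/T)).

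| T (h) | Share of AUC0-48 in first 24 h | Ratio |
|---|---|---|
| 2 | 0.9998 | 2.00 |
| 3 (projected) | 0.9961 | 1.99 |
| 4 | 0.9846 | 1.97 |
| 6 | 0.9412 | 1.88 |
| 12 | 0.8000 | 1.60 |
| 24 | 0.6667 | 1.33 |

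A one-compartment oral model at steady state, with assumed absorption rates of 0.5 to 4 per hour, gives 1.986 to 1.992 at T = 3 and 1.847 to 1.879 at T = 6. Immediate absorption is therefore not driving the result.

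**Step 2: the 12 h form**

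Ratio = 4 × (1 − 2^(−12/T)) / (1 − 2^(−48/T)). At T = 3 this is 4 × 0.9375 = 3.75.

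**Step 3: on the projected exposure at 2 mg QOD (T = 3)**

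- Over 48 h: 0.2 / 48 = 0.0042 µM.
- 24 h form: 0.2 × 0.9961 / 24 = 0.0083 µM.
- 12 h form: 0.2 × 0.9375 / 12 = 0.0156 µM.

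**Step 4: Fluctuation**

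With Cmin near zero (2^(−16) of the peak at T = 3), Fluctuation is 0.05 / 0.00417 = 12.0 over 48 h and 0.05 / 0.00830 = 6.0 with the 24 h form. In the oral model at T = 3 it falls from 5.71 to 2.88 at the slowest absorption and from 9.31 to 4.68 at the fastest. It is about halved in each case.

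**Step 5: the interval AUC**

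At T = 3, AUC0-24 is 99.6% of AUC0-48, a shortfall of about 0.4%. The 24 h label is wrong for QOD, but the AUC value hardly moves. The material error is in C_ave and whatever is divided by it.

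**Step 6: effect on a schedule comparison**

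The TG B cohorts 2 mg QD and 4 mg QOD (Protocol Table 1) both deliver 4 mg per 48 h. Assuming dose-proportional PK, their true C_ave is equal. The 24 h form is right for QD and 1.99 times too high for QOD, so the QOD cohort would appear to have about twice the average concentration.

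**The case against.** The strongest reply is that this is a leftover template line that a pharmacokineticist would read past. The AUC0-tau row already refers to one dosing interval, which is 48 h for QOD, and the protocol uses AUC0-48 elsewhere. This partly stands: the distortion arises only if the C_ave parenthesis is followed as written. But the C_ave row has no interval wording to fall back on, the AUC0-tau row contradicts its own label, and computing C_ave over 48 h would depart from the written definition.

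A second reply is that little depends on these parameters. The secondary endpoints and the analysis sections of both documents name six plasma parameters (Cmax, Tmax, Cmin, AUC0-t, t1/2, Cl/F). C_ave, AUC0-tau and Fluctuation are not among them, and the public text of SAP Appendix A lists no display of them. This stands and limits the consequence.

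Three stronger readings are tempting and not supported:

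- *That dose selection is compromised.* Protocol Section 4.1.2 rests the expansion doses on safety and tolerability, and Section 1.6.2 ties the TG B choice to DLTs. PK is one input to the aggregate review in Section 4.1.1, but no text uses C_ave or Fluctuation for a dose decision.
- *That the plan divides 48 h of exposure by 24 h.* It does not; that would give exactly 2.00 at every half-life. The written form takes both AUC and divisor over 24 h, which is why the factor depends on half-life.
- *That TG E1 is also affected.* TG E starts on QOD, but TG E1 takes whichever regimen Part 3 settles on (Protocol Section 4.1.4), so its schedule is not fixed.

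**Conclusion.** The C_ave definition is wrong as written for QOD subjects, and Fluctuation inherits the error. Taken literally, the 24 h form overstates QOD C_ave 1.99-fold and roughly halves Fluctuation at the projected 3 h half-life; the 12 h form, which matches no INCB059872 regimen, would overstate C_ave 3.75-fold. The size rests on a projected half-life and first-order elimination. The 24 h factor falls to 1.88 at an assumed 6 h and 1.33 at an assumed 24 h, so it would remain material over that range. The affected groups are the Part 1 QOD cohorts, TG A2, B1 and B2, and TG E at its starting regimen. This is a minor point: it concerns descriptive parameters outside the named PK endpoints and is worth correcting because any QOD versus QD comparison of C_ave or Fluctuation would otherwise mislead.

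**What to change.** In Protocol Appendix C, define tau as the assigned dosing interval (24 h for QD, 48 h for QOD), define AUC0-tau over that interval, set C_ave = AUC0-tau/tau, and delete the 12 h option. Repeat the definition in SAP Section 8.

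This is an edit of a line or two in each document. It changes no sampling, dosing or visit, and the named PK endpoints stay as they are.

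One limit remains. Timed sampling ends at 6 h (Protocol Table 10). Under the mono-exponential model with T = 3, about 75% of AUC0-48 falls within those 6 h (about 50% with T = 6). The rest will depend on extrapolation or a predose value whichever interval is used, and SAP Section 8 should say which.
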